Progressive disease (PD) can be determined without evaluation of all sites of disease based on the greatest transverse diameter (GTD), area or SPD for target lesions, evaluation of unequivocal progression in non-target lesions, or observation of a new lesion within the available radiographic or clinical assessments.

Appendix 4

Revised Response Criteria for Malignant Lymphoma (cont.)

TOO SMALL TO MEASURE (TSTM) LESION CATEGORY

Any target lesion findings identified on baseline images, which at a subsequent timepoint decreases in size to <5 mm in any dimension, should be categorized as TSTM. The lesion, node, or mass should be assigned measurements of 5 × 5 mm (for the GTD and the short axis) on the source document for the purposes of calculating the area. If that lesion increases in size to ≥5 mm in any dimension afterwards, its true size (GTD and short axis) should be recorded. The purpose of the assigned value for the measurement is the acknowledgment that small findings are not accurately measured.

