Appendix 4 Revised Response Criteria for Malignant Lymphoma (cont.)

Timepoint Response

Target Lesions	Non-Target Lesions	New Lesions ^a	Timepoint Response
CR	CR	No	CR
CR	SD	No	PR
CR	UE	No	UE
PR	UE	No	UE
PR	CR	No	PR
PR	SD	No	PR
SD	UE	No	UE
SD	CR	No	SD
SD	SD	No	SD
PD	Any	Yes/No	PD
Any	PD	Yes/No	PD
Any	Any	Yes	PD
UE	Non-PD	No	UE
UE	UE	No	UE
CR	NA ^c	No	CR
PR	NA ^c	No	PR
SD	NA ^c	No	SD
NA ^b	SD	No	SD
NA ^b	CR	No	CR
NA ^b	UE	No	UE
NA ^b	NA ^c	No	UE

CR=complete response; NA=not applicable; PD=progressive disease; PR=partial response; SD=stable disease; UE=unable to evaluate.

Note: Modified from Cheson BD, Pfistner B, Juweid ME, et al. Revised response criteria for malignant lymphoma. J Clin Oncol 2007;25:579–86.

^a Identification of new lesions at a post-baseline time point will result in a response assessment of PD. If an identified new lesion subsequently becomes UE, the timepoint response will be recorded as PD unless the new lesion has proven to have resolved.

^b No target lesions identified at baseline.

^c No non-target lesions identified at baseline.

Appendix 4

Revised Response Criteria for Malignant Lymphoma (cont.)

Response should be determined on the basis of radiographic and clinical evidence of disease. For the end-of-treatment response assessment, an FDG-PET will be performed 6–8 weeks after the last study treatment. Assessment of PET should follow the criteria described by Juweid et al. 2007, which is presented in the table Response Definitions for Clinical Trials.

COMPLETE RESPONSE

- Complete disappearance of all detectable clinical evidence of disease and disease-related symptoms if present before therapy
- Typically ¹⁸F-fluorodeoxyglucose (FDG)–avid lymphoma: in patients with no pre-treatment positron emission tomography (PET) scan or when the PET scan was positive before therapy, a post-treatment residual mass of any size is permitted as long as it is PET negative.
- Variably FDG-avid lymphomas/FDG avidity unknown: in patients without a pre-treatment PET scan, or if a pre-treatment PET scan was negative, all lymph nodes and nodal masses must have regressed on CT to normal size (≤ 1.5 cm in their greatest transverse diameter for nodes > 1.5 cm before therapy). Previously involved nodes that were 1.1 to 1.5 cm in their long axis and > 1.0 cm in their short axis before treatment must have decreased to ≤ 1.0 cm in their short axis after treatment.

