- Bone marrow assessment is irrelevant for determination of a PR if the sample was positive before treatment. However, if positive, the cell type should be specified (e.g., large-cell lymphoma or small neoplastic B cells). Patients who achieve a CR by the above criteria but who have persistent morphologic bone marrow involvement will be considered partial responders. If the bone marrow was involved before therapy and a clinical CR is achieved, but with no bone marrow assessment after treatment, patients should be considered partial responders.
- No new sites of disease should be observed.
- Typically FDG-avid lymphoma: for patients with no pre-treatment PET scan or if the PET scan was positive before therapy, the post-treatment PET should be positive in at least one previously involved site.
- Variably FDG-avid lymphomas/FDG-avidity unknown: for patients without a pre-treatment PET scan, or if a pre-treatment PET scan was negative, CT criteria should be used.

In patients with follicular lymphoma or mantle-cell lymphoma, a PET scan is only indicated with one or at most two residual masses that have regressed by more than 50% on CT; those with more than two residual lesions are unlikely to be PET negative and should be considered partial responders.

Appendix 4

Revised Response Criteria for Malignant Lymphoma (cont.)

STABLE DISEASE

- A patient is considered to have SD when he or she fails to attain the criteria needed for a CR or PR but does not fulfill those for progressive disease (PD) (see Relapsed Disease [after Complete Response] or Progressive Disease [after Partial Response or Stable Disease]).
- Typically FDG-avid lymphomas: the PET should be positive at prior sites of disease with no new areas of involvement on the post-treatment CT or PET.
- Variably FDG-avid lymphomas/FDG-avidity unknown: for patients without a pre-treatment PET scan or if the pre-treatment PET was negative, there must be no change in the size of the previous lesions on the post-treatment CT scan.

RELAPSED DISEASE (AFTER COMPLETE RESPONSE) OR PROGRESSIVE DISEASE (AFTER PARTIAL RESPONSE OR STABLE DISEASE)

Lymph nodes should be considered abnormal if the long axis is more than 1.5 cm, regardless of the short axis. If a lymph node has a long axis of 1.1 to 1.5 cm, it should only be considered abnormal if its short axis is more than 1.0. Lymph nodes $\leq 1.0 \times \leq 1.0$ cm will not be considered as abnormal for relapse or progressive disease.

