- Appearance of any new lesion > 1.5 cm in any axis during or at the end of therapy, even if other lesions are decreasing in size. Increased FDG uptake in a previously unaffected site should only be considered relapsed or progressive disease after confirmation with other modalities. In patients with no prior history of pulmonary lymphoma, new lung nodules identified by CT are mostly benign. Thus, a therapeutic decision should not be made solely on the basis of the PET without histologic confirmation.
- At least a 50% increase from nadir in the SPD of any previously involved nodes, or in a single involved node, or the size of other lesions (e.g., splenic or hepatic nodules). To be considered PD, a lymph node with a diameter of the short axis < 1.0 cm must increase by $\geq 50\%$ and to a size of 1.5×1.5 cm or > 1.5 cm in the long axis.
- At least a 50% increase in the longest diameter of any single previously identified node > 1 cm in its short axis.
- Lesions should be PET positive if observed in a typical FDG-avid lymphoma or the lesion was PET positive before therapy unless the lesion is too small to be detected with current PET systems (< 1.5 cm in its long axis by CT).

Measurable extranodal disease should be assessed in a manner similar to that for nodal disease. For these recommendations, the spleen is considered nodal disease. Disease that is only assessable (e.g., pleural effusions, bone lesions) will be recorded as present

Appendix 4

Revised Response Criteria for Malignant Lymphoma (cont.)

or absent only, unless, while an abnormality is still noted by imaging studies or physical examination, it is found to be histologically negative.

In clinical trials where PET is unavailable to the vast majority of participants, or where PET is not deemed necessary or appropriate for use (e.g., a study involving patients with mucosa-associated lymphoid tissue lymphoma), response should be assessed as above but only using CT scans. However, residual masses should not be assigned unconfirmed complete response status but should be considered partial responses.

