Appendix 4 Revised Response Criteria for Malignant Lymphoma (cont.)

Response Definitions for Clinical Trials (Revised International Working Group Criteria 2007)

Response	Definition	Nodal Masses	Spleen, Liver	Bone Marrow
CR	Disappearance of all evidence of disease	a) FDG-avid or PET positive prior to therapy; mass of any size permitted if PET negative b) Variably FDG-avid or PET negative; regression to normal size on CT	No palpable, nodules; nodules disappeared	Infiltrate cleared on repeat biopsy; if indeterminate on morphology and immunohistochemistry; bone marrow should be negative
PR	Regression of measurable disease and no new sites	A \geq 50% decrease in SPD of up to six largest dominant masses; no increase in size of other nodes a) FDG-avid or PET positive prior to therapy; one or more PET positive at previously involved site b) Variably FDG-avid or PET negative; regression on CT	A \geq 50% decrease in SPD of nodules (for single nodule in the greatest transverse diameter); no increase in size of liver or spleen	Irrelevant if positive prior to therapy; cell type should be specified
SD	Failure to attain CR/PR or PD	a) FDG-avid or PET positive prior to therapy; PET positive at prior sites of disease and no new sites on CT or PET b) Variably FDG-avid or PET negative; no change in size of previous lesions on CT		
Relapsed disease or PD	Any new lesion or increase by \geq 50% of previously involved sites from nadir	Appearance of a new lesion(s) $>$ 1.5 cm in any axis, \geq 50% increase in SPD of more than one node, or \geq 50% increase in longest diameter of previously identified node $>$ 1 cm in short axis Lesions PET positive if FDG-avid lymphoma or PET positive prior to therapy	50% increase from nadir in the SPD of any previous lesions	New or recurrent involvement

CR=complete response; CT=computed tomography; FDG = 18 F-fluorodeoxyglucose; PD=progressive disease; PET=positron-emission tomography; PR=partial response; SPD=sum of the product of the diameters.

Excerpted from: Juweid ME, Stroobants S, Hoekstra OS, et al. Use of positron emission tomography for response assessment of lymphoma: consensus of the Imaging Subcommittee of International Harmonization Project in Lymphoma. J Clin Oncol 2007;25:571–8.

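### Appendix 4 gives two rules for when a new lymphoma lesion is progression, one with a 1.5 cm limit and one without, so PFS and DOR dates can differ for the same scan

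*Combined protocol and SAP*

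**What the plan says.** Section 6.6.1 makes ORR and PFS the primary efficacy endpoints and sends both lymphoma types to Appendix 4. Section 6.6.2 does the same for DOR. The investigator makes the assessment.

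Three places in Appendix 4 make a new lesion progressive disease (PD) without a size limit:

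- **Timepoint Response table.** Any target status, any non-target status and a Yes for new lesions gives PD. Footnote a adds: "Identification of new lesions at a post-baseline time point will result in a response assessment of PD".
- **Reporting Conventions, Unable to Evaluate category.** PD may rest on "observation of a new lesion within the available radiographic or clinical assessments".
- **Response Definitions for Clinical Trials table, PD row, Definition column.** It opens "Any new lesion or increase by".

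Two places set a limit:

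- **Relapsed or Progressive Disease section.** "Appearance of any new lesion > 1.5 cm in any axis during or at the end of therapy". The same bullet accepts new FDG uptake in a previously unaffected site only after confirmation with other modalities.
- **The same PD row, Nodal Masses column.** It repeats the threshold of more than 1.5 cm in any axis.

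The Relapsed or Progressive Disease section also says which nodes are abnormal. For a long axis of 1.1 to 1.5 cm, "it should only be considered abnormal if its short axis is more than 1.0". Nodes no larger than 1.0 x 1.0 cm "will not be considered as abnormal for relapse or progressive disease".

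**The concern.** The two sets of statements classify the same new finding differently, and both are current text. The Response Definitions table carries both wordings in one row.

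The call of PD sets the event date for PFS and ends DOR. About 50 sites are planned (Section 3.1.1), and each investigator would choose between the readings alone. The situation is foreseeable. Section 3.3.4 describes new radiographic lesions in responding patients that held immune cells and no viable tumor. Section 4.5.5.1 asks for FDG-PET at every lymphoma response assessment, so the question of unconfirmed new uptake will also arise.

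**Working it through.** No sample-size or power figure is involved. The check applies each rule to example findings.

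**1. Classification under each rule**

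| New finding | Timepoint table and footnote a | Relapsed or Progressive Disease section |
|---|---|---|
| Node 1.4 x 1.2 cm | PD | Abnormal (long axis within 1.1 to 1.5 cm, short axis above 1.0 cm) but not above 1.5 cm, so not PD |
| Extranodal lesion 1.2 cm | PD | Not PD |
| Lesion 1.6 cm | PD | PD on size |
| Node 0.9 x 0.9 cm | Not abnormal under the node sentence; footnote a is silent | Not PD |
| New FDG uptake, not confirmed by another modality | PD if identification is enough | Not PD |

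The clear size conflict covers new nodes with a long axis of 1.1 to 1.5 cm and a short axis above 1.0 cm, and new extranodal lesions of 1.5 cm or less. Nodes no larger than 1.0 x 1.0 cm are outside it.

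**2. What category remains if the finding is not PD**

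Take the 1.4 x 1.2 cm node under the 1.5 cm rule.

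- Complete response fails, because all detectable disease must be gone.
- Partial response fails, because its criteria allow no new disease sites, of any size.
- Stable disease is the remainder category in general, but for typically FDG-avid lymphoma it also excludes new areas of involvement on CT or PET, again of any size.

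So the 1.5 cm reading leaves no category that fits cleanly in FDG-avid disease.

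**3. Effect on ORR**

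By step 2, a patient with such a lesion is not a responder at that timepoint under either rule. The readings can separate on ORR only along one path: the table calls PD, the new lesion later resolves, and a confirmed response follows.

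**4. Effect on PFS and DOR dates**

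Under the table the event falls on the first scan showing the lesion. Under the progression section it falls on a later scan at which the lesion qualifies, or on another event, or does not occur. Section 4.5.5.1 schedules scans every two cycles to Cycle 8 (2 x 21 = 42 days) and every fourth cycle after that (4 x 21 = 84 days). These are the gaps between scheduled scans. They are not a lower bound on the shift, because unscheduled scans are allowed, and a follow-up scan after two cycles or earlier is required for patients treated past possible pseudoprogression.

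**The case against.** The best defense is that the timepoint table is only a look-up. Its target and non-target columns take their thresholds from the text that follows, so its new-lesion column could do the same. The stable disease text also refers the reader to the progression section for what counts as PD. This is a natural reading, but Appendix 4 never states it, and two things tell against it. The unlimited wording recurs in the Reporting Conventions and in the Definition column. The appendix also has significant new effusions or ascites recorded as new lesions, and a rule on axis length cannot describe those, so the table's category is wider than the size rule.

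A second defense is that Section 6.6.2 already plans an immune-related analysis for lymphoma. That analysis is secondary and does not settle the primary reading.

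Several stronger inferences are tempting and do not stand:

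- **That ORR and the expansion thresholds in Table 3 are at risk.** One patient is 1/14 = 7.1 points in Hodgkin's disease (10 of 14 needed) and 1/12 = 8.3 points in non-Hodgkin's lymphoma (6 of 12 needed). This is per-patient arithmetic only. Partial response bars any new site under both readings, no affected patient can be shown, and Section 6.1 also weighs feasibility, biomarkers and safety in expansion.
- **That the node sentence is a third rule for PD.** It defines when a node is abnormal and does not say that a new abnormal node is progression.
- **That every small new node is in dispute.** The lower bound for nodes excludes the smallest.
- **That event dates move by at least one scan interval.** The unscheduled scans in step 4 rule this out.
- **That small new nodes or uptake are especially prone to immune flare.** Section 3.3.4 does not refer to size.

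**Conclusion.** The point holds as an inconsistent endpoint rule: followed as written, Appendix 4 allows two different event dates for the same lymphoma scan. It concerns PFS and DOR in the Hodgkin's and non-Hodgkin's cohorts, which total 26 patients at the Table 3 minima (14 + 12). ORR is affected only along the single path in step 3.

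The number of patients affected and the size of the date shift cannot be estimated, because the documents give no frequency for new lesions in the disputed range. The conclusion assumes that no text outside these documents, such as a reading manual, fixes the meaning of the new-lesion column. The change should be made, since the repair is short and the rule defines a primary endpoint.

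**What to change.** Amend footnote a so that a Yes for new lesions has one definition, tied to the Relapsed or Progressive Disease section. It should cover:

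- the size rule for nodes and for extranodal lesions;
- PET-only uptake, after confirmation by another modality;
- significant new effusions, as the appendix already describes;
- new or recurrent marrow involvement, which the Response Definitions table lists under PD and which has no axis to measure.

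State the timepoint category for a new lesion that does not yet qualify, and how PD is dated if it later does.

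Then align the remaining text with that definition: the Reporting Conventions sentence, the exclusion of new sites under partial response, the exclusion of new areas under stable disease, the sentence on nodes of 1.1 to 1.5 cm, and the Definition column of the PD row. Changing footnote a alone would leave a clash: a patient with shrinking targets and a 1.4 cm new node could be coded No and read as partial response from the table, against the partial response criteria.

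The cost is a short appendix edit, plus a check of lymphoma reads already made against the single rule.

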Appendix 4 Revised Response Criteria for Malignant Lymphoma (cont.)

Response Definitions for Clinical Trials (Revised International Working Group Criteria 2007)

Response	Definition	Nodal Masses	Spleen, Liver	Bone Marrow
CR	Disappearance of all evidence of disease	a) FDG-avid or PET positive prior to therapy; mass of any size permitted if PET negative b) Variably FDG-avid or PET negative; regression to normal size on CT	No palpable, nodules; nodules disappeared	Infiltrate cleared on repeat biopsy; if indeterminate on morphology and immunohistochemistry; bone marrow should be negative
PR	Regression of measurable disease and no new sites	A \geq 50% decrease in SPD of up to six largest dominant masses; no increase in size of other nodes a) FDG-avid or PET positive prior to therapy; one or more PET positive at previously involved site b) Variably FDG-avid or PET negative; regression on CT	A \geq 50% decrease in SPD of nodules (for single nodule in the greatest transverse diameter); no increase in size of liver or spleen	Irrelevant if positive prior to therapy; cell type should be specified
SD	Failure to attain CR/PR or PD	a) FDG-avid or PET positive prior to therapy; PET positive at prior sites of disease and no new sites on CT or PET b) Variably FDG-avid or PET negative; no change in size of previous lesions on CT		
Relapsed disease or PD	Any new lesion or increase by \geq 50% of previously involved sites from nadir	Appearance of a new lesion(s) $>$ 1.5 cm in any axis, \geq 50% increase in SPD of more than one node, or \geq 50% increase in longest diameter of previously identified node $>$ 1 cm in short axis Lesions PET positive if FDG-avid lymphoma or PET positive prior to therapy	50% increase from nadir in the SPD of any previous lesions	New or recurrent involvement

CR=complete response; CT=computed tomography; FDG = 18 F-fluorodeoxyglucose; PD=progressive disease; PET=positron-emission tomography; PR=partial response; SPD=sum of the product of the diameters.

Excerpted from: Juweid ME, Stroobants S, Hoekstra OS, et al. Use of positron emission tomography for response assessment of lymphoma: consensus of the Imaging Subcommittee of International Harmonization Project in Lymphoma. J Clin Oncol 2007;25:571–8.

Appendix 5 Modified Response Evaluation Criteria in Solid Tumors

Conventional response criteria may not be adequate to characterize the anti-tumor activity of immunotherapeutic agents like atezolizumab, which can produce delayed responses that may be preceded by initial apparent radiological progression, including the appearance of new lesions. Therefore, modified response criteria have been developed that account for the possible appearance of new lesions and allow radiological progression to be confirmed at a subsequent assessment.

Modified Response Evaluation Criteria in Solid Tumors (RECIST) is derived from RECIST, Version 1.1 (v1.1) conventions¹ and immune-related response criteria² (irRC). When not otherwise specified, RECIST v1.1 conventions will apply.

Modified RECIST and RECIST v1.1: Summary of Changes

	RECIST v1.1	Modified RECIST
New lesions after baseline	Define progression	New measurable lesions are added into the total tumor burden and followed.
Non-target lesions	May contribute to the designation of overall progression	Contribute only in the assessment of a complete response
Radiographic progression	First instance of $\geq 20\%$ increase in the sum of diameters or unequivocal progression in non-target disease	Determined only on the basis of measurable disease

RECIST=Response Evaluation Criteria in Solid Tumors.

A. DEFINITIONS OF MEASURABLE/NON-MEASURABLE LESIONS

All measurable and non-measurable lesions should be assessed at Screening and at the protocol-specified tumor assessment timepoints. Additional assessments may be performed, as clinically indicated for suspicion of progression.

¹ Eisenhauer et al. Eur J Cancer 2009;45: 228–47; Topalian et al. N Engl J Med 2012;366:2443–54; and Wolchok et al., Clin Can Res 2009;15:7412–20.

² Wolchok et al. Clin Can Res 2009;15:7412–20; Nishino et al. J Immunother Can 2014;2:17; Nishino et al. Clin Can Res 2013;19:3936–43.

Appendix 5

Modified Response Evaluation Criteria in Solid Tumors (cont.)

A.1 MEASURABLE LESIONS

Tumor Lesions. Tumor lesions must be accurately measured in at least one dimension (longest diameter in the plane of measurement is to be recorded) with a minimum size as follows:

- 10 mm by computed tomography (CT) or magnetic resonance imaging (MRI) scan (CT/MRI scan slice thickness/interval no greater than 5 mm)
- 10-mm caliper measurement by clinical examination (lesions that cannot be accurately measured with calipers should be recorded as non-measurable)

Malignant Lymph Nodes. To be considered pathologically enlarged and measurable, a lymph node must be ≥ 15 mm in the short axis when assessed by CT scan (CT scan slice thickness recommended to be no greater than 5 mm). At baseline and follow-up, only the short axis will be measured and followed.

A.2 NON-MEASURABLE LESIONS

Non-measurable tumor lesions encompass small lesions (longest diameter < 10 mm or pathological lymph nodes with short axis ≥ 10 but < 15 mm), as well as truly non-measurable lesions. Lesions considered truly non-measurable include leptomeningeal disease, ascites, pleural or pericardial effusion, inflammatory breast disease, lymphangitic involvement of skin or lung, peritoneal spread, and abdominal mass/abdominal organomegaly identified by physical examination that is not measurable by reproducible imaging techniques.

A.3 SPECIAL CONSIDERATIONS REGARDING LESION MEASURABILITY

Bone lesions, cystic lesions, and lesions previously treated with local therapy require particular comment, as outlined below.

Bone Lesions

Bone scan, positron emission tomography (PET) scan, or plain films are not considered adequate imaging techniques for measuring bone lesions. However, these techniques can be used to confirm the presence or disappearance of bone lesions.

Lytic bone lesions or mixed lytic–blastic lesions, with identifiable soft tissue components, that can be evaluated by cross-sectional imaging techniques such as CT or MRI can be considered as measurable lesions if the soft tissue component meets the definition of measurability described above.

Blastic bone lesions are non-measurable.

Appendix 5

Modified Response Evaluation Criteria in Solid Tumors (cont.)

Cystic Lesions

Lesions that meet the criteria for radiographically defined simple cysts should not be considered as malignant lesions (neither measurable nor non-measurable) since they are, by definition, simple cysts.

Cystic lesions thought to represent cystic metastases can be considered as measurable lesions, if they meet the definition of measurability described above. However, if non-cystic lesions are present in the same patient, these are preferred for selection as target lesions.

Lesions with Prior Local Treatment

Tumor lesions situated in a previously irradiated area or in an area subjected to other loco-regional therapy are usually not considered measurable unless there has been demonstrated progression in the lesion. Study protocols should detail the conditions under which such lesions would be considered measurable.

B. TUMOR RESPONSE EVALUATION

B.1 DEFINITIONS OF TARGET/NON-TARGET LESIONS

Target Lesions

When more than one measurable lesion is present at baseline, all lesions up to a maximum of five lesions total (and a maximum of two lesions per organ) representative of all involved organs should be identified as target lesions and will be recorded and measured at baseline. This means that, for instances in which patients have only one or two organ sites involved, a maximum of two lesions (one site) and four lesions (two sites), respectively, will be recorded. Other lesions (albeit measurable) in those organs will be recorded as non-measurable lesions (even if the size is > 10 mm by CT scan).

Target lesions should be selected on the basis of their size (lesions with the longest diameter) and be representative of all involved organs, but in addition, should lend themselves to reproducible repeated measurements. It may be the case that, on occasion, the largest lesion does not lend itself to reproducible measurement, in which circumstance, the next largest lesion that can be measured reproducibly should be selected.

Lymph nodes merit special mention since they are normal anatomical structures that may be visible by imaging even if not involved by tumor. As noted above,

Appendix 5

Modified Response Evaluation Criteria in Solid Tumors (cont.)

pathological nodes that are defined as measurable and may be identified as target lesions must meet the criterion of a short axis of ≥ 15 mm by CT scan. Only the short axis of these nodes will contribute to the baseline sum. The short axis of the node is the

diameter normally used by radiologists to judge if a node is involved by solid tumor. Nodal size is normally reported as two dimensions in the plane in which the image is obtained (for CT, this is almost always the axial plane; for MRI, the plane of acquisition may be axial, sagittal, or coronal). The smaller of these measures is the short axis. For example, an abdominal node that is reported as being 20 mm \times 30 mm has a short axis of 20 mm and qualifies as a malignant, measurable node. In this example, 20 mm should be recorded as the node measurement. All other pathological nodes (those with short axis ≥ 10 mm but < 15 mm) should be considered non-target lesions. Nodes that have a short axis of < 10 mm are considered non-pathological and should not be recorded or followed.

Lesions irradiated within 3 weeks prior to Cycle 1 Day 1 may not be counted as target lesions.

Non-Target Lesions

All other lesions (or sites of disease), including pathological lymph nodes, should be identified as non-target lesions and should also be recorded at baseline. Measurements are not required.

It is possible to record multiple non-target lesions involving the same organ as a single item on the eCRF (e.g., “multiple enlarged pelvic lymph nodes” or “multiple liver metastases”).

After baseline, changes in non-target lesions will contribute only in the assessment of complete response (i.e., a complete response is attained only with the complete disappearance of all tumor lesions, including non-target lesions) and will not be used to assess progressive disease.

New Lesions

During the study, all new lesions identified and recorded after baseline must be assessed at all tumor assessment timepoints. New lesions will also be evaluated for measurability with use of the same criteria applied to prospective target lesions at baseline per RECIST, (e.g., non-lymph node lesions must be ≥ 10 mm; see note for new lymph node lesions below). Up to a maximum of five new lesions total (and a maximum of two lesions per organ), all with measurements at all timepoints, can be included in the

Appendix 5

Modified Response Evaluation Criteria in Solid Tumors (cont.)

tumor response evaluation. New lesion types that would not qualify as target lesions per RECIST cannot be included in the tumor response evaluation.

New lesions that are not measurable at first appearance but meet measurability criteria at a subsequent timepoint will be measured from that point on and contribute to the sum of longest diameters (SLD), if the maximum number of 5 measurable new lesions being followed has not been reached.

B.2 CALCULATION OF SUM OF THE DIAMETERS

A sum of the diameters (longest for non-nodal lesions, short axis for nodal lesions) for all target lesions will be calculated as a measure of tumor burden.

The sum of the diameters is calculated at baseline and at each tumor assessment for the purpose of classification of tumor responses.

Sum of the Diameters at Baseline: The sum of the diameters for all target lesions identified at baseline prior to treatment on Day 1.

Sum of the Diameters at Tumor Assessment: For every on-study tumor assessment collected per protocol or as clinically indicated the sum of the diameters at tumor assessment will be calculated using tumor imaging scans. All target lesions selected at baseline and up to five new measurable lesions (with a maximum of two new lesions per organ) that have emerged after baseline will contribute to the sum of the diameters at tumor assessment. Hence, each net percentage change in tumor burden per assessment with use of modified RECIST accounts for the size and growth kinetics of both old and new lesions as they appear.

Note: In the case of new lymph nodes, RECIST v1.1 criteria for measurability (equivalent to baseline target lesion selection) will be followed. That is, if at first appearance the short axis of a new lymph node lesion ≥ 15 mm, it will be considered a measurable new lesion and will be tracked and included in the SLD. Thereafter, the lymph node lesion will be measured at subsequent timepoints and measurements will be included in the SLD, even if the short axis diameter decreases to < 15 mm (or even < 10 mm). However, if it subsequently decreases to < 10 mm, and all other lesions are no longer detectable (or have also decreased to a short axis diameter of < 10 mm if lymph nodes), then a response assessment of CR may be assigned.

If at first appearance the short axis of a new lymph node is ≥ 10 mm and < 15 mm, the lymph node will not be considered measurable but will still be considered a new lesion. It will not be included in the SLD unless it subsequently becomes measurable (short axis diameter ≥ 15 mm).

Appendix 5

Modified Response Evaluation Criteria in Solid Tumors (cont.)

The appearance of new lymph nodes with diameter < 10 mm should not be considered pathological and not considered a new lesion.

B.3 RESPONSE CRITERIA

Timepoint Response

It is assumed that at each protocol-specified timepoint, a response assessment occurs. [Table 1](#) provides a summary of the overall response status calculation at each timepoint for patients who have measurable disease at baseline.

Complete Response (CR): Disappearance of all target and non-target lesions. Lymph nodes that shrink to < 10 mm short axis are considered normal.

Partial Response (PR): At least a 30% decrease in the sum of the diameters of all target and all new measurable lesions, taking as reference the baseline sum of diameters, in the absence of CR.

Note: the appearance of new measurable lesions is factored into the overall tumor burden, but *does not automatically qualify as progressive disease* until the sum of the diameters increases by $\geq 20\%$ when compared with the sum of the diameters at nadir.

Stable Disease (SD): Neither sufficient shrinkage to qualify for PR nor sufficient increase to qualify for PD, taking as reference the smallest sum of the diameters while on study.

Progressive Disease (PD): At least a 20% increase in the sum of diameters of all target and selected new measurable lesions, taking as reference the smallest sum on study (nadir SLD; this includes the baseline sum if that is the smallest on study). In addition to the relative increase of 20%, the sum must also demonstrate an absolute increase of at least 5 mm.

Impact of New Lesions on Modified RECIST

New lesions alone do not qualify as progressive disease. However, their contribution to total tumor burden is included in the sum of the diameters, which is used to determine the overall modified RECIST tumor response.

